7.2.2.5.5 Thyroid

Thyroid panel is to be performed centrally according to the Visit Evaluation Schedule outlined in [Table 7-1](#). For details of the thyroid panel, refer to [Table 7-5](#).

7.2.2.5.6 Urine protein/creatinine ratio

UPC is to be performed centrally according to the Visit Evaluation Schedule outlined in [Table 7-1](#).

7.2.2.5.7 24-hour urine collection

24-hour urine collection is to be performed according to the Visit Evaluation Schedule outlined in [Table 7-1](#). Urine will be collected over a 24-hour period using materials supplied by the central lab. The analysis of the 24-hour urine collection will be performed centrally.

7.2.2.5.8 Pregnancy testing

Serum pregnancy tests are required at screening and end of treatment for women of child-bearing potential.

Monthly urine pregnancy testing is required during treatment for women of child-bearing potential. Urine pregnancy tests for use during on-site visits will be supplied by the central lab and will be performed locally during site visits on Day 1 of Cycles 2 through 6. After Cycle 6, women of child-bearing potential will be required to perform monthly at-home urine pregnancy tests. At-home pregnancy test kits will be supplied by the investigator. Patients who administer the urine pregnancy test at home will complete a simple diary with the dates and outcome of the urine pregnancy test while on study treatment. Patients should be instructed to bring the diary with them to every visit.

Please refer to the [Section 5.3](#) for the definition of women of child-bearing potential.

7.2.2.6 Cardiac assessments

7.2.2.6.1 Electrocardiogram (ECG)

A standard 12-lead ECG will be performed locally at the time points indicated in [Table 7-6](#) below. ECGs should be done after the patient has been resting for 5-10 min prior to each time point.

Unscheduled ECGs may be performed at the discretion of the investigator at any time during the study and as clinically indicated.

Table 7-6 Local ECG collection plan

Cycle/Visit	Day	Time point	ECG Type
Screening	-7 to -1	Anytime	12 Lead
3	1	Anytime	12 Lead
5	1	Anytime	12 Lead
7	1	Anytime	12 Lead
9	1	Anytime	12 Lead
11	1	Anytime	12 Lead
13	1	Anytime	12 Lead
Cycle 16 and every 3 rd cycle (i.e. cycle 19, 22, 25, etc.) and End of Treatment	1	Anytime	12 Lead
Unscheduled		Anytime	12 Lead

Interpretation of the tracing must be made by a qualified physician and documented on the ECG CRF page. Each ECG tracing should be labeled with the study number, patient initials (where regulations permit), patient number, date, and kept in the source documents at the study site. Clinically significant abnormalities present at screening should be reported on the Medical

History CRF page. Clinically significant findings must be discussed with Novartis prior to enrolling the patient in the study. New or worsened clinically significant findings occurring after informed consent must be recorded on the Adverse Events CRF page. Refer to Table 6.2 for additional monitoring requirements if the QTcF interval is \geq 500 msec.

[figure not shown]
7.2.2.6.2 Cardiac imaging- multiple gated acquisition (MUGA) scan or echocardiogram (ECHO)

Cardiac imaging will be performed locally by MUGA scan or ECHO in order to assess the left ventricular ejection fraction. This assessment will be performed according to the schedule indicated in [Table 7-7](#) below.

Unscheduled cardiac imaging may be performed at the discretion of the investigator at any time during the study and as clinically indicated. Patients should be closely monitored for signs and symptoms of congestive heart failure. In particular, patients at risk of cardiac dysfunction or with prior anthracycline exposure may warrant more frequent monitoring.

Table 7-7 Local cardiac imaging collection plan

Cycle/Visit	Day	Time point
Screening	-7 to -1	Anytime
5	1	Anytime
11	1	Anytime
Cycle 16 and every 6 th cycle thereafter (i.e., cycles 22, 28 etc.) and End of Treatment	1	Anytime
Unscheduled	Anytime	Anytime

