Chest x-rays and ultrasound should not be used to measure tumor lesions.

Post-baseline imaging assessments

Imaging assessments as described in [Table 7-3](#) should be performed at the time points specified using the same imaging modality used at screening. Imaging assessments for response evaluation will be performed every 8 weeks (\pm 7 days) during the first year, and every 12 weeks (\pm 7 days) thereafter until study treatment discontinuation for disease progression, death, lost to follow-up, withdrawal of consent or the end of the study. Imaging assessments should be scheduled using the treatment start date (Cycle 1 Day 1) as the reference date (not the previous tumor assessment date), and should be respected regardless of whether the study treatment is temporarily withheld or unscheduled assessments performed.

Additional imaging assessments may be performed at any time during the study at the investigator's discretion to support the efficacy evaluations for a subject, as necessary. Clinical suspicion of disease progression at any time requires a physician examination and imaging assessments to be performed promptly rather than waiting for the next scheduled imaging assessment.

Each lesion that is measured at screening must be measured by the same method and when possible, the same local radiologist/physician throughout the study so that the comparison is consistent. If an off-schedule imaging assessment is performed because progression is suspected, subsequent imaging assessments should be performed in accordance with the original imaging schedule.

Partial Response (PR) and Complete Response (CR) must be confirmed by repeat assessments performed not less than 4 weeks and after the criteria for response are first met. Positron Emission Tomography (PET)/CT may be used only if the CT component is of similar diagnostic quality as a CT performed without PET, including the utilization of oral and i.v. contrast media. At the discretion of the Investigators, FDG-PET scans may be performed to document progressive disease per RECIST 1.1 ([Appendix 2](#)). If possible, a single radiologist should perform all tumor response evaluations for an individual patient. Any lesions in previously irradiated areas should not be considered measurable unless they have experienced progression since the radiotherapy. Any pre-existing radiographic findings which may mimic metastatic disease and any prior radiotherapy should be recorded in the eCRF.

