10.5.3.4 Other safety data

ECG

- Local 12-lead ECGs including HR, PR, QRS, QT, and QTcF intervals will be obtained for each subject at baseline, during the study treatment period and at the end of treatment. ECG data will be read and interpreted locally.
- The number and percentage of patients with notable ECG interval values and change from baseline ECG parameters by time point will be summarized in the Safety set.
- All collected data will be presented in data listings; notable values and abnormality finding will be flagged in the listing.

Echocardiogram/MUGA

- Local echocardiogram or MUGA will be obtained for each subject at baseline, during the study treatment period and at the end of treatment.
- Ejection fraction values will be classified based on NCI-CTCAE v4.03 and a shift table will be prepared for the Safety set to summarize the distribution of individual worst on-treatment values vs. the corresponding baseline values.
- All collected data will be presented in data listings and notable values will be flagged.

Vital signs

- Data on vital signs will be tabulated and listed, notable values will be flagged.

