2.8.4.3 Additional Analyses: Echocardiogram/MUGA

Data handling

In case the study requires ECHO/MUGA replicates at any assessment, the average of the LVEF at that assessment should be used in the analyses.

Data analysis

Local echocardiogram or MUGA will be obtained for each patient will be obtained at baseline, during the study treatment period and at the end of treatment. The number and percentage of patients with notable post-baseline values of left ventricular ejection fraction (LVEF) based on NCI-CTCAE v4.03 will be summarized on the Safety Set:

- Grade 2: LVEF between ≥ 40 and ≤ 50 % and/or decrease from baseline between ≥ 10 and < 20 %
- Grade 3: LVEF between < 40 and ≤ 20 % and/or decrease from baseline between > 20 %
- Grade 4: LVEF < 20 %

In addition, the following notable post-baseline values will also be described on the Safety Set:

- Number of patients with new LVEF (%) $< 50\%$
- Number of patients with new LVEF (%) $< 50\%$ and decrease $> 10\%$
- Number of patients with new LVEF (%) $< 50\%$ and decrease $> 20\%$

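### LVEF may be measured by MUGA or ECHO with no rule keeping a patient on one method, so a method switch can create or hide an apparent fall in the descriptive LVEF summary

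*Protocol*

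**What the plan says.** Protocol 7.2.2.6.2 gives the method in one sentence: "Cardiac imaging will be performed locally by MUGA scan or ECHO in order to assess the left ventricular ejection fraction". Table 7-7 schedules one assessment at screening, Cycles 5, 11 and 16, every sixth cycle after that and End of Treatment, plus unscheduled scans. Protocol 10.5.3.4 repeats the choice: "Local echocardiogram or MUGA will be obtained for each subject at baseline, during the study treatment period and at the end of treatment". It also plans that "a shift table will be prepared for the Safety set to summarize the distribution of individual worst on-treatment values vs. the corresponding baseline values". The screening list in Protocol 7.1.1.3 names both methods as alternatives.

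SAP 2.1.1 takes baseline as the last assessment on or before the start of treatment, without reference to method. SAP 2.8.4.3 defines its categories partly by change from that baseline:

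- The first graded category reads "Grade 2: LVEF between ≥ 40 and ≤ 50 % and/or decrease from baseline between ≥ 10 and < 20" percent.
- Grade 3 has an absolute band "and/or decrease from baseline between > 20" percent.
- Two of the three additional categories combine a new value below 50% with a decrease of more than 10% or more than 20%.
- Grade 4 and the remaining additional category use absolute values only.

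The section contains no flag, exclusion, separate summary or sensitivity analysis for a change of method.

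For tumor imaging, Protocol 7.2.1 requires later scans to be done "using the same imaging modality used at screening". That rule covers the procedures in Table 7-3, which does not list cardiac imaging.

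**The concern.** A change from baseline is interpretable when both readings come from the same instrument. If screening was by MUGA and Cycle 5 by ECHO, the difference contains any real change, the ordinary repeat error and the disagreement between methods. The SAP would count the total as a change in LVEF. The error can run either way: a switch may push a stable patient over the 10-point line or mask a real fall. The protocol's shift table adds to this because it takes the worst on-treatment value, so one discordant low reading is enough to classify a patient.

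With no control arm, there is no parallel group in which the same artefact would appear and could be subtracted. At stake is how the LVEF part of the safety report is read.

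**Working it through.** **No figure to reproduce.** The plan states no precision, error rate or expected count for LVEF. The check is therefore a reading of the text, followed by an illustration on assumed inputs.

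**Reading.** Protocol 7.1.1.3, 7.2.2.6.2 with Table 7-7, and 10.5.3.4 each name the two methods as alternatives, and none ties a patient to one. SAP 2.1.1 and 2.8.4.3 do not mention method when defining baseline or change. Followed as written, the plan allows a mixed-method pair and analyses it like any other.

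**Illustration.** Assume no true change, one post-baseline reading, and decreases read as percentage points. Let SD be the standard deviation of the difference between two readings, and let the offset be the downward shift caused by the switch. Then

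P(apparent fall ≥ 10) = 1 − Φ((10 − offset) / SD).

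The SDs, offsets and switching shares are all assumptions; none is in the documents.

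| Pair | SD | Offset | P(fall ≥ 10) | Excess over same method | × 1/4 switching, per 100 | × 1/3 switching, per 100 |
|---|---|---|---|---|---|---|
| Same method | 5 | 0 | 1 − Φ(2.00) = 2.3% | – | – | – |
| Switched | 7 | 0 | 1 − Φ(1.43) = 7.7% | 5.4 | 1.3 | 1.8 |
| Switched | 10 | 0 | 1 − Φ(1.00) = 15.9% | 13.6 | 3.4 | 4.5 |
| Switched | 7 | 5 | 1 − Φ(0.71) = 23.8% | 21.5 | 5.4 | 7.2 |
| Switched | 10 | 5 | 1 − Φ(0.50) = 30.9% | 28.6 | 7.1 | 9.5 |

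The excess thus runs from 1.3 to 9.5 per 100 patients scanned at that visit.

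**Switches in both directions.** The last two rows assume that every switch lowers the reading. If half the switches carry +5 and half −5:

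- SD 7: (23.8% + 1.6%) / 2 = 12.7%, where 1.6% = 1 − Φ(15/7).
- SD 10: (30.9% + 6.7%) / 2 = 18.8%, where 6.7% = 1 − Φ(15/10).

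With one third switching, the excess becomes (12.7 − 2.3)/3 = 3.5 and (18.8 − 2.3)/3 = 5.5 per 100, in place of 7.2 and 9.5.

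**Dependence on the switching share.** With SD 7 and offsets of 0 to 5, 10% switching gives 2.8 to 4.4 apparent falls per 100 against 2.3 with none, an excess of 0.5 to 2.1. If nobody switches, the excess is zero.

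**Per patient enrolled.** Cycle 5 Day 1 falls 112 days after the start. Table 10-1 uses an overall median PFS of 5 months, or 152.2 days. If PFS is exponential and stands in for time on treatment, exp(−ln 2 × 112/152.2) = 0.60 of patients reach that scan. The one-third range of 1.8 to 9.5 then becomes about 1.1 to 5.7 per 100 enrolled at Cycle 5. Later scans and the End of Treatment scan give further opportunities.

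**The case against.** The best defence is that silence is not permission. Protocol 10.5.3.4 can be read as one method per subject, sites often keep to one method by habit, and the documents give no switch rate. The cardiac-imaging row of Table 7-1 does not appear in the text available for review, and the eCRF was not available, so a note on method or a field recording it may exist. This stands as a limit on confidence. It does not supply the missing rule, since 7.2.2.6.2 is the main text and sets none. Nor is the tumor-imaging rule a contradiction: it serves lesion measurement for the primary endpoint and only shows that the sponsor applies the principle elsewhere.

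Four stronger readings are tempting, and the documents do not support them.

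- *The SAP averages ECHO with MUGA.* The clause is conditional: "In case the study requires ECHO/MUGA replicates at any assessment, the average of the LVEF at that assessment should be used in the analyses". Table 7-7 requires no replicates, so nothing planned is averaged.
- *Falls from baseline define the cardiac safety results.* They define part of the LVEF summary. Grade 4 and the plain below-50% category are absolute, although a shift between methods can also move a value across an absolute cut. ECG results are separate, and SAP 2.8.1.1 builds AESIs from reported events grouped by MedDRA terms.
- *An artefact would drive treatment decisions.* The cardiac block of Table 6-2 concerns QTcF only. No LVEF-specific rule exists there, and the general adverse-event rows turn on clinical significance.
- *The rates of 24% to 31% are an estimate.* They follow from an assumed 5-point offset that always runs downward.

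**Conclusion.** The gap holds, in a limited form. Nothing visible keeps a patient on the screening LVEF method, and SAP 2.8.4.3 does not distinguish a mixed-method pair from a same-method pair. A switch can therefore create or hide an apparent fall in a single-arm descriptive summary. PFS and the ECG and AE/AESI tabulations are not derived from these counts.

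The size is unknown. Under the assumptions above it is very roughly 1 to 10 false falls of at least 10 points per 100 patients scanned at one visit. The upper end is lower if switches go both ways, and the excess is nil if sites do not switch. Severity is minor: no hypothesis is tested on LVEF, but the remedy costs little.

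**What to change.** In Protocol 7.2.2.6.2, require that the method used at screening be used for that patient's later LVEF assessments where feasible, and that the method be recorded at each assessment.

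In SAP 2.8.4.3, compute change from baseline only from same-method pairs, and list or summarize values obtained after a switch separately. Apply the same restriction to any baseline-to-worst shift table.

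No procedure is added. The cost is slightly less scheduling freedom at sites and a few unpaired values left out of the change-from-baseline counts. Amendment 2 reports 8 patients still on treatment, so from that date the protocol sentence can reach few scans. The SAP rule is the more useful half for data already collected, provided that the method was captured.

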7.2.4 Resource utilization

Not applicable.

7.2.5 Patient reported outcomes

Patient reported outcomes (PROs) provide patients, physicians, and payers with valuable information about the impact of a given treatment on all facets of the patient's life. PRO measures for use in clinical trial assess symptoms, functioning, health related quality of life and quality of life or a combination of these outcomes.

Both questionnaires (EQ-5D-5L and FKSI-DRS) will be provided electronically (ePRO) and are to be completed by the patient.

Both questionnaires must be completed during the screening phase within 7 days before the first dose of study medication (pazopanib) only after patient eligibility is confirmed, or on Cycle 1 Day 1 predose. During the treatment phase, both questionnaires should be completed on Day 1

of every cycle until Cycle 7 and then every 2nd cycle until Cycle 16 and then every 3rd cycle thereafter until the end of study medication treatment.

The questionnaires should be completed in the language most familiar to the patient.

The investigator or designee will administer both questionnaires under the following conditions:

- upon arrival to the clinic, before the patient has their evaluation visit with the treating oncologist
- upon arrival to the clinic, before the patient has their radiological tumor evaluations (CT scan or MRI).

The patient should be given sufficient space and time to complete the questionnaires. The site staff should check the questionnaire for completeness and encourage the patient to complete any missing responses.

Completed questionnaire(s) and any unsolicited comments written by the patient should be reviewed and assessed by the investigator for responses which may indicate potential AEs or SAEs before any clinical study examinations. This assessment should be documented in the study source records.

7.2.5.1 Euro QOL-EQ-5D-5L (EQ-5D-5L)

The EQ-5D-5L is a general health status and health utility measure ([Rabin 2001](#)). It measures 5 dimensions of health state: mobility, self-care, usual activities, pain/discomfort, and anxiety/depression each assessed by a single question on a three-point ordinal scale. It also includes a VAS scale to measure health state. The EQ-5D-5L will be included in this study for the purpose of the computation of utilities that can be used in health economic studies. This instrument has been used extensively in cancer studies and published results from these studies support its validity and reliability ([Pickard 2007](#)).

7.2.5.2 FKSI-DRS

The Functional Assessment of Cancer Therapy - Kidney Symptom Index, Disease Related Symptoms (FKSI-DRS) is a set of items selected which was developed and validated to specifically assess symptoms experienced by patients with advanced kidney cancer ([Cella 2007](#)). Item development was conducted using both clinician and patient input to determine the 9 most important symptoms and concerns of people being treated for advanced kidney cancer. These 9 items were then validated by administering the symptom index to patients diagnosed with advanced kidney cancer. The symptoms covered by the 9-item FKSI-DRS include fatigue, pain, weight loss, dyspnea, cough, fever and hematuria. The FKSI-DRS will be scored according to the developers' instructions. A difference of 2-3.0 points is suggested by the developers to correspond to a meaningful difference in treatment effects using the 9 question tool.

8 Safety monitoring and reporting

8.1 Adverse events

8.1.1 Definitions and reporting

An adverse event is defined as the appearance of (or worsening of any pre-existing) undesirable sign(s), symptom(s), or medical condition(s) that occur after patient's signed informed consent has been obtained.

Abnormal laboratory values or test results occurring after informed consent constitute adverse events only if they induce clinical signs or symptoms, are considered clinically significant, require therapy (e.g., hematologic abnormality that requires transfusion or hematological stem cell support), or require changes in study medication(s).

Adverse events that begin or worsen after informed consent should be recorded in the Adverse Events CRF. Conditions that were already present at the time of informed consent should be recorded in the Medical History page of the patient's CRF. Adverse event monitoring should be continued for at least 30 days following the last dose of study treatment. Adverse events (including lab abnormalities that constitute AEs) should be described using a diagnosis whenever possible, rather than individual underlying signs and symptoms. When a clear diagnosis cannot be identified, each sign or symptom should be reported as a separate Adverse Event.

Adverse events will be assessed and graded according to the Common Terminology Criteria for Adverse Events (CTCAE) version 4.03.

Grade 1 to 5 will be used to characterize the severity of the Adverse Event.

If CTCAE grading does not exist for an adverse event, the severity of mild, moderate, severe, and life-threatening, death related to the AE corresponding respectively to Grades 1 - 5, will be used. Information about any deaths (related to an Adverse Event or not) will also be collected through a Death form.

The occurrence of adverse events should be sought by non-directive questioning of the patient (subject) during the screening process after signing informed consent and at each visit during the study. Adverse events also may be detected when they are volunteered by the patient (subject) during the screening process or between visits, or through physical examination, laboratory test, or other assessments. As far as possible, each adverse event should be evaluated to determine:

1. The severity grade (CTCAE Grade 1-5)
2. Its duration (Start and end dates)
3. Its relationship to the study treatment (Reasonable possibility that AE is related: No, Yes)
4. Action taken with respect to study treatment (none, dose adjusted, temporarily interrupted, permanently discontinued, unknown, not applicable)
5. Whether medication or therapy was given (no concomitant medication/non-drug therapy, concomitant medication/non-drug therapy)
6. Whether it is serious, where a serious adverse event (SAE) is defined as in [Section 8.2.1](#) and which seriousness criteria have been met

7. Outcome (not recovered/not resolved, recovered/resolved, recovering/resolving, recovered/resolved with sequelae, fatal, unknown)

If the event worsens the event should be reported a second time in the CRF noting the start date when the event worsens in toxicity. For grade 3 and 4 adverse events only, if improvement to a lower grade is determined a new entry for this event should be reported in the CRF noting the start date when the event improved from having been Grade 3 or Grade 4.

All adverse events should be treated appropriately. If a concomitant medication or non-drug therapy is given, this action should be recorded on the Adverse Event CRF.

Once an adverse event is detected, it should be followed until its resolution or until it is judged to be permanent, and assessment should be made at each visit (or more frequently, if necessary) of any changes in severity, the suspected relationship to the study treatment, the interventions required to treat it, and the outcome.

Progression of malignancy (including fatal outcomes), if documented by use of appropriate method (i.e. as per RECIST criteria), should not be reported as a serious adverse event.

Adverse events separate from the progression of malignancy (example, deep vein thrombosis at the time of progression or hemoptysis concurrent with finding of disease progression) will be reported as per usual guidelines used for such events with proper attribution regarding relatedness to the drug.

